11.2 Diet and lifestyle

On day -1 of each period, a standardized low-fat dinner will be served after confinement. Then the subjects will not take any food or drinks (except water) for approximately 10 h (i.e. overnight).

On day 1 of each study period, before investigational product administration, all subjects will receive a high-fat and high-caloric breakfast starting 30 min pre-dose and will complete their breakfast within 30 min from start. A standardized lunch and dinner will be served at approximately 5 h and 12 h post-dose (at approximately 13:00 and 20:00). Water will be allowed as desired except for 1 h before and 1 h after investigational product administration.

For the 4 h following the administration, when not involved in study activities, the subjects will remain seated. They will not be allowed to lie down.

In order to maintain an adequate hydration, the subjects will be encouraged to drink at least 150 mL of still mineral water every 2 h for 5 h post-dose, starting at 1 h post-dose. One cup of coffee or tea will be allowed after lunch and dinner only; any other coffee, tea or food containing xanthines (i.e. coke, chocolate, etc.), alcohol and grapefruit will be forbidden. In particular, grapefruit will be forbidden for 24 h before the first investigational product administration until the end of the study. The subjects will be allowed to smoke 3 cigarettes during confinement (1 cigarette after each meal, with the exclusion of breakfast).

During confinement, routine ambulant daily activities will be strongly recommended.

11.2.1 Restrictions

During each study period, the subjects will be confined from the evening preceding the investigational product administration (study day -1) until the morning of day 2.

During confinement, hazardous, strenuous or athletic activities will not be permitted.

12 DESCRIPTION OF SPECIFIC PROCEDURES

12.1 Physical examination

Full physical examinations will be performed at the screening and Final Visit/ ETV. Information about the physical examination will be recorded by the investigator. Any abnormalities will be recorded.

Significant findings/illnesses, reported after the start of the study and that meet the definition of an AE (see \S 16), will be recorded in the subject source documents.

Date of the physical examination, overall investigator's interpretation (as normal or abnormal and, if abnormal, clinically significant or not clinically significant) and clinically significant abnormalities (if any) will be reported in the individual case report forms (CRFs).

12.1.1 Body weight

Body weight will be recorded at screening and Final Visit/ETV.

Subjects will be weighed (kg) lightly clothed without shoes. Height will be measured at screening only and BMI will be recorded. BMI will be calculated as weight [kg]/(height [m] x height [m]).

12.1.2 Vital signs

Subjects' blood pressure (BP) and heart rate (HR) will be measured by the investigator or his deputy after 5 min at rest (sitting position) at:

- Screening
- In each study period at pre-dose (0), 1.5 and 24 h post-dose. The 24 h measurement of Period 3 will correspond to the final assessment
- ➢ At ETV, if applicable

12.1.3 ECGs

12-Leads ECGs will be performed in supine position at:

- Screening
- In each study period at 24 h post-dose. The 24 h recording of Period 3 will correspond to the final assessment
- ➢ At ETV, if applicable

Date/time of the ECG recording, overall investigator's interpretation (as normal or abnormal and, if abnormal, clinically significant or not clinically significant) and clinically significant abnormalities (if any) will be reported in the individual CRFs. All clinically significant abnormalities after the screening visit will be recorded as AEs (see § 16). Hard copies of the ECGs will be attached to the individual CRFs.

12.2 Clinical laboratory assays

Samples of blood (12.5 mL) and urine will be collected. The following laboratory analyses will be performed at the screening visit:

Haematology

Leukocytes and leukocyte differential count (percentage values and absolute values), erythrocytes, haemoglobin (conv. units), haemoglobin (IS units), haematocrit, MCV, MPV, MCH, MCHC, thrombocytes.

Blood chemistry

Electrolytes: sodium, potassium, calcium, chloride, inorganic phosphorus **Enzymes:** alkaline phosphatase, γ-GT, AST, ALT **Substrates/metabolites:** total bilirubin, creatinine, glucose, urea, uric acid, total cholesterol, triglycerides **Proteins:** total proteins

Urine analysis

Urine chemical analysis (stick): pH, specific weight, appearance, colour, nitrites, proteins, glucose, urobilinogen, bilirubin, ketones, haematic pigments, leukocytes Urine sediment (analysis performed only if positive): leukocytes, erythrocytes, flat cells, round cells, crystals, cylinders, mucus, bacteria, yeast, Trichomonas

Serum virology Hepatitis B (HBs antigen), Hepatitis C (HCV antibodies), HIV 1/2 (HIV Ag/Ab combo).

A urine drug test will be performed at the clinical centre at screening and on day -1 of each period, using a urine multi-drug kit. The following drugs will be assessed: cocaine, amphetamine, methamphetamine, cannabinoids (delta-9-tetrahydrocannabinol - THC), opiates and ecstasy.

The same analyses, with the exception of urine drug test and virology will be performed at the Final Visit/ETV.

Date/time of samples collection, overall investigator's interpretation (as normal or abnormal and, if abnormal, clinically significant or not clinically significant) and clinically significant findings (if any) will be reported in the individual CRFs. All clinically significant abnormalities after the screening visit will be recorded as AEs (see § 16). Hard copies of the laboratory print-outs will be attached to the CRFs.

12.3 Sampling for pharmacokinetic analysis

12.3.1 Venous blood sampling

Venous blood samples (9 mL) will be collected from a forearm vein on days 1-2 of each period at the following times:

pre-dose (0) and 6, 15, 30, 45 min and 1, 1.25, 1.5, 2, 2.5, 3, 4, 6, 8, 12, 16 and 24 h post-dose

Actual sampling times for each subject will be recorded in the individual CRFs. Deviations in actual sampling times should not exceed the recommended ranges reported in the following table.

Sampling time	Tolerance range
Pre-dose (0)	Within 40 min before IMP administration*
6 min, 15 min	0 min
30 min	$\pm 1 \min$
45 min	$\pm 2 \min$
1, 1.25, 1.5 h	$\pm 3 \min$
2, 2.5, 3, 4, 6, 8 h	± 5 min
12, 16, 24 h	± 10 min

Table 12.3.1.1 Tolerance ranges for the scheduled sampling times

*Before the high-fat, high caloric breakfast (§ 8.1.3).

Any deviations outside the recommended ranges will be verified through Data Clarification Forms (DCFs) and will not automatically lead to the exclusion of the concerned subjects from the PK Set (see § 15.1).

Blood samples for PK analysis will be collected using an indwelling catheter with switch valve. The cannula will be rinsed, after each sampling, with about 1 mL of sterile saline solution containing 20 I.U./mL Na-heparin. The first 2 mL of blood will be discarded at each collection time to avoid contamination of the sample with heparin.

The remaining 7 mL will be collected from the catheter and transferred with a syringe into heparinised tubes (Li-heparin).

The samples will be stored on ice for a maximum of 20 min and then centrifuged at 4° C for 10 min at 2500 g to obtain plasma. Each plasma sample will be immediately divided into 3 aliquots, P1, P2 and P3, in pre-labelled polypropylene tubes, and stored frozen at \leq -20° C.

If any clinical assessment, such as vital signs measurement or ECG recording, is foreseen at the same time-point as blood sampling for PK analysis, blood collection will be performed at the scheduled time. However, vital signs and ECG parameters can be influenced by the blood sampling. Therefore, these assessments can be performed within 30 min before pre-dose (0 h) and within 10 min before the other scheduled PK time-points. Since vital signs measurement

and ECG recording will be performed for safety reasons only, deviations from the planned time schedule will be considered not relevant.

12.3.2 Analytics

Sildenafil free base and its metabolite N-desmethyl-sildenafil will be determined in plasma at Ardena Bioanalysis B.V., the Netherlands, using a validated LS-MS/MS method. Further analyses for the determination of sildenafil free base and its metabolite N-desmethyl-sildenafil will be conducted at Syneos Health Clinique Inc., Canada using a validated LS-MS/MS method.

The bioanalysis will be performed in compliance with GCP and in accordance with the applicable principles of Good Laboratory Practice (GLP), as defined by OECD, in a GLP compliant facility.

The method validation report and the analytical report will be attached to the final report.

12.3.3 Labelling, storage and transport of samples

12.3.3.1 Samples labelling

Each sample tube will be clearly and unequivocally identified with a label resistant to the storage temperature and reporting:

Study code	Study CRO-PK-20-346 - Sponsor code 20CH-SDF10
Subject number	001-036
Tube identification	P1/P2/P3
Period	1 or 2 or 3
Scheduled sampling time	as h; see § 12.3.1

12.3.3.2 Samples storage and transport

During the study the samples will be stored at \leq -20° C. At the end of each collection day, P1 and P2/P3 aliquots will be stored in separate freezers.

All P1 aliquots, packed in sufficient solid CO₂, will be shipped by an authorised courier from CROSS Research Phase I Unit, Switzerland, to the analytical laboratory (Ardena Bioanalysis B.V., the Netherlands; § 21.3).

P1 aliquots will remain stored at the analytical laboratory for a maximum time of 3 months after a QA audited bioanalytical report is issued. Afterwards, the samples will either be destroyed or returned or stored for a longer period in agreement with the Sponsor. In case the sample destruction is chosen, a certificate of destruction will be provided to the Sponsor.

The counter-samples (P2/P3 aliquots) will remain stored at CROSS Research S.A., Switzerland. These samples could either be:

sent to the laboratory for reanalysis should this become necessary for analytical reasons or if any problems occur during the delivery of P1 aliquots, or

- sent to a different laboratory, i.e., Syneos Health Clinique Inc., Canada, for reanalysis should this become necessary for analytical reasons
- destroyed at an authorised site, or
- transferred to the Sponsor upon written request, or
- ▶ stored at CROSS Research S.A., for a maximum time of 5 years

The counter-samples (P2/P3 aliquots) will also remain stored at the analytical laboratory for a maximum time of 3 months after a QA audited bioanalytical report is issued. Afterwards, the samples will either be destroyed or returned or stored for a longer period in agreement with the Sponsor. In case the sample destruction is chosen, a certificate of destruction will be provided to the Sponsor.

No analyses different from those stated in this protocol and agreed by the subjects when signing the informed consent form will be performed unless a new informed consent and a new approval from the Ethical Committee is obtained. The subjects may ask to destroy their own samples at any time.

12.4 Total number of samples and blood withdrawn

During the study the following volume of blood will be collected:

For routine laboratories analysis: Screening visit: 12.5 mL Final Visit/ETV: 12.5 mL

For PK analysis:

Treatment T1:	17 samples x 9 mL = 153 mL
Treatment T2:	17 samples x 9 mL = 153 mL
Treatment R:	17 samples x 9 mL = 153 mL

In total 484 mL of blood (not exceeding a normal blood donation) will be withdrawn from each subject.

Study protocol CRO-PK-20-346 Sponsor code 20CH-SDF10 Sildenafil IBSA 100 mg oral film BA Fed Final version 3.0, 10MAY2021

13 ASSIGNMENT OF STUDY TREATMENT

13.1 Randomisation

The randomisation list will be computer-generated by the Biometry Unit of the Clinical Contract Research Organization (CRO), using the PLAN procedure of the SAS[®] version 9.3 (TS1M1) (18) or higher (the actual version will be stated in the final report). The randomisation list will be supplied to the study site before study start. The randomisation list will be attached to the final clinical study report.

13.2 Treatment allocation

Subjects will be assigned to one sequence of the three treatments according to the randomisation list and to the 3-way cross-over design.

Randomisation number will be given to the subjects on study day -1, period 1, and will be used to assign the treatment sequence, as detailed above. Treatment assignment will be performed according to CRO SOP 03.78 and will be detailed in a study manual.

13.3 Blinding

This is an open study. No masking procedure will be applied.

14 EVALUATION PARAMETERS

14.1 Study variables

14.1.1 Primary variables

> C_{max} , AUC_{0-t} and AUC_{0-∞} (if feasible) of plasma sildenafil.

14.1.2 Secondary variables

- > t_{max} , F_{rel} and, if feasible, $t_{1/2}$ and λ_z of plasma sildenafil;
- > C_{max} , AUC_{0-t}, t_{max} , F_{rel} and, if feasible, AUC_{0- ∞}, $t_{1/2}$, and λ_z of plasma N-desmethyl-sildenafil;
- TEAEs, vital signs (BP, HR), body weight, physical examinations, clinical laboratory parameters, ECG.

14.2 Pharmacokinetic assessments

14.2.1 Pharmacokinetic parameters

The following PK parameters will be measured and/or calculated for plasma sildenafil and N-desmethyl-sildenafil using the validated software Pharsight Corporation Phoenix WinNonlin[®] version 6.3 (18) or higher (the actual version will be stated in the final report):

C _{max} :	Maximum plasma concentration
t _{max} :	Time to achieve C _{max}
λ_z :	Terminal elimination rate constant, calculated, if feasible, by log-linear regression using at least 3 points
t _{1/2} :	Half-life, calculated, if feasible, as $ln2/\lambda_z$
AUC _{0-t} :	Area under the concentration-time curve from administration to the last observed concentration time t, calculated with the linear trapezoidal method
$AUC_{0-\infty}$:	Area under the concentration-time curve extrapolated to infinity, calculated, if feasible, as $AUC_{0-t} + C_t/\lambda_z$, where C_t is the last measurable drug concentration
%AUC _{extra} :	Percentage of the residual area (C_t/λ_z) extrapolated to infinity in relation to the total AUC _{0-∞} , calculated, if feasible as $100 \times [(C_t/\lambda_z)/AUC_{0-\infty}]$
F _{rel} :	Relative bioavailability, calculated as ratio AUC _{0-t} (Test)/ AUC _{0-t} (Reference)

Study protocol CRO-PK-20-346 Sponsor code 20CH-SDF10 Sildenafil IBSA 100 mg oral film BA Fed Final version 3.0, 10MAY2021

The sampling schedule is considered adequate if the ratio $AUC_{0-t}/AUC_{0-\infty}$ equals or exceeds a factor of 0.8 (i.e. if %AUC_{extra} is <20%) for more than 80% of the individual PK profiles. This assures that AUC_{0-t} covers a sufficient percentage of the theoretical total extent of exposure.

The quality of log-linear regression (and, consequently, the reliability of the extrapolated PK parameters) should be demonstrated by a determination coefficient $R^2 > 0.8$. Individual extrapolated parameters, when considered unreliable, will be reported as NC (not calculated).

14.3 Safety assessments

Safety and general tolerability of the investigational products will be based on TEAEs, physical examinations, body weight, vital signs, ECG and routine haematology, blood chemistry and urinalysis laboratory tests.

15 STATISTICAL METHODS

The data documented in this study and the parameters measured will be evaluated and compared using classic descriptive statistics, i.e. geometric mean (PK data only), arithmetic mean, SD, CV (%), minimum, median and maximum values for quantitative variables, and frequencies for qualitative variables.

Not available data will be evaluated as "missing values". The statistical analysis of demographic and safety data will be performed using SAS[®] version 9.3 (TS1M1) (18) or higher (the actual versions will be stated in the final report).

The statistical analysis of PK parameters will be performed using Phoenix WinNonlin[®] version 6.3 (18) or higher and SAS[®] version 9.3 (TS1M1) or higher.

15.1 Analysis Sets

15.1.1 Definitions

A subject will be defined as screened after the signature of the informed consent, regardless of the completion of all the screening procedures.

A subject will be defined as eligible if he meets all the inclusion/exclusion criteria. Otherwise he will be defined as a screen failure.

A subject will be defined as enrolled in the study if he is included in the interventional part of the study. The enrolment is performed through randomised allocation to a treatment sequence.

An eligible but not enrolled subject will be defined as a reserve.

A subject will be defined as randomised in the study when he is assigned to a randomised treatments sequence.

The following analysis sets will be defined:

- Enrolled set: all enrolled subjects. This analysis set will be used for demographic, baseline and background characteristics
- Safety set: all subjects who receive at least one dose of IMP. This analysis set will be used for the safety analyses
- PK set 1: all randomised subjects who fulfil the study protocol requirements in terms of T1 and R IMP intake and have evaluable PK data readouts for the planned T1 vs R comparison, with no major deviations that may affect the PK results. This analysis set will be used for the statistical comparison of T1 and R treatments
- PK set 2: all randomised subjects who fulfil the study protocol requirements in terms of T2 and R IMP intake and have evaluable PK data readouts for the planned T2 vs R comparison, with no major deviations that may affect the PK results. This analysis set will be used for the statistical comparison of T2 and R treatments.

PK set 3: all randomised subjects who fulfil the study protocol requirements in terms of T1 and T2 IMP intake and have evaluable PK data readouts for the planned T1 vs T2 comparison, with no major deviations that may affect the PK results. This analysis set will be used for the statistical comparison of T1 and T2 treatments.

Each subject will be coded by the CRO Biometry Unit as valid or not valid for the Safety set and the PK sets. Subjects will be evaluated according to the treatment they actually receive.

15.1.2 Reasons for exclusion from the PK set before the bioanalysis

For each of the planned treatment comparisons, reasons for the exclusion of subjects from the PK sets are the following:

- vomiting and diarrhoea after drug intake which could render the plasma concentrationtime profile unreliable in the respective study periods
- intake of concomitant medications which could render the plasma concentration-time profile unreliable in the respective study periods
- AEs which could render the plasma concentration-time profile unreliable in the respective study periods
- administration errors which could render the plasma concentration-time profile unreliable in the respective study periods
- other events which could render the plasma concentration-time profile unreliable in the respective study periods

If one of these events occurs, it will be noted in the CRF as the study is being conducted.

15.1.3 Reasons for exclusion from the PK set after the bioanalysis

Exclusion of subjects on the basis of PK reasons is possible only for:

- subjects with lack of any measurable concentrations or only very low plasma concentrations for the Reference product. A subject is considered to have very low plasma concentrations if his AUC is less than 5% of the Reference route geometric mean AUC (which should be calculated without inclusion of data from the outlying subject)
- subjects with implausible concentrations (i.e. different from the known, expected concentration profiles) for the Reference product. The exclusion of these subjects must be justified on the basis of sound scientific reasons and mutually agreed between the CRO and the Sponsor
- > subjects with non-zero baseline concentrations > 5% of C_{max}

The samples from the subjects excluded from the PK sets should still be assayed and the results listed. Subjects should not be excluded from the PK sets if the AUC_{0-t} covers less than 80% of the $AUC_{0-\infty}$.

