9.2 Discussion of design

The study has been designed taking into consideration the following US Department of Health and Human Services Food and Drug Administration (FDA) Guidance for Industry: *Food-Effect Bioavailability and Fed Bioequivalence Studies*, Center for Drug Evaluation and Research CDER December 2002 BP (13); *Bioavailability and Bioequivalence Studies Submitted in NDAs or INDs - General Considerations*, CDER March 2014 Biopharmaceutics - *Draft* (14), *Bioavailability Studies Submitted in NDAs or INDs*, CDER February 2019 Clinical Pharmacology - *Draft* (15).

The sample size for this study was not calculated through any statistical calculation due to the lack of previous informative data on the bioavailability of Viagra[®] 100 mg film-coated tablet administered in fed conditions.

The dose of 100 mg of sildenafil was chosen on the basis of the clinical practice and the recommended dose regimen of 25-100 mg.

The investigation will be performed under fed conditions and the results of the study will be used for the Sildenafil oral film registration procedure in the US.

Each randomised subject will be allocated to one sequence of treatments according to a computer generated randomisation list (see § 13.1) and to the 3-way cross-over design.

An open-label design is used since the primary end-point of the study is based on objective measurements of sildenafil in blood. The outcome variables are not influenced by the subjects or Investigator being aware of the administered products.

Blood sampling time-points were selected on the basis of the known PK profile of the sildenafil and are the same as for previous Phase I studies (7, 8, 16). Wash-out interval between subsequent administrations is based on sildenafil half-life and is the same used in the other Phase I studies.

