15.2 Sample size and power considerations

Thirty-six (36) healthy men will be enrolled in the study. No formal calculation was performed due to the lack of previous informative data on the bioavailability of Viagra[®] 100 mg film-coated tablet administered in fed conditions. Discontinued subjects will not be replaced.

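### Section 15.1.3 allows subjects to be dropped after bioanalysis for an implausible Reference profile: no threshold, Reference only, not decided blind, so the primary T1/R and T2/R ratios are exposed

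*Protocol*

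**What the plan says.** Protocol section 15.1.3 governs removal from the PK sets after the assay results exist. Its list is closed: "Exclusion of subjects on the basis of PK reasons is possible only for" the three reasons that follow. The first covers absent or very low Reference concentrations and has a number: "A subject is considered to have very low plasma concentrations if his AUC is less than 5% of the Reference route geometric mean AUC". The third, a pre-dose concentration above 5% of Cmax, is also numeric and is not tied to one product. The second is the one at issue: "subjects with implausible concentrations (i.e. different from the known, expected concentration profiles) for the Reference product". Its only condition is that the exclusion "must be justified on the basis of sound scientific reasons and mutually agreed between the CRO and the Sponsor". The section adds a transparency rule: "The samples from the subjects excluded from the PK sets should still be assayed and the results listed".

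Other sections bear on this:
- Section 13.3: the study is open and nothing is masked.
- Sections 13.1 and 15.1.1: the CRO Biometry Unit generates the randomisation list and also codes each subject as valid or not for the PK sets.
- Section 15.2, on the Reference tablet given with food: "No formal calculation was performed due to the lack of previous informative data on the bioavailability of" that product under those conditions. Section 9.2 says the same.
- Section 6.2: the only fed-state figures are a mean tmax delay of 60 min and a mean Cmax reduction of 29%, with no measure of spread.
- Section 15.5.2: the analysis is an ANOVA on log-transformed data with 90% confidence intervals for T1/R, T1/T2 and T2/R.

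**The concern.** The bullet makes membership of the primary analysis depend on the outcome, and on one side of the ratio only. Because the list is closed, an equally odd T1 or T2 profile must stay in, so the denominator of T1/R and T2/R can be trimmed and the numerator cannot. A rule that names the Reference also cannot be applied without knowing which period was the Reference period, so as written it cannot be operated blind. Nothing requires the decision before the T1 and T2 results, or the ratios, have been seen.

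The comparison standard is an expected profile, yet the protocol gives no range for a fed Reference profile and says the informative data are lacking. Two people following the text in good faith could decide differently about the same subject.

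Section 6.4 intends the results for US registration. The intervals rest on 36 subjects, with no replacement of drop-outs, so one or two exclusions matter.

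**Working it through.** The protocol states no power or error rate, so there is no design figure to reproduce. As an input check, the earlier study's Cmax point estimate should be the geometric mean of its limits: sqrt(90.33 × 109.68) = 99.54%, against 99.53% stated in section 6.2.1.

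**Within-subject SD (fasting Cmax, 90% CI 90.33-109.68%).** Half-width on the log scale: ln(109.68/90.33)/2 = 0.0970. For a two-way crossover, s = half-width / t(0.95, n−2) × sqrt(n/2).
- n = 53: 0.0970/1.675 × sqrt(26.5) = 0.298, CV 30.5%.
- n = 54: 0.301, CV 30.8%.

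Section 6.2.1 gives 54 men; the event percentages in section 6.3 fit a denominator of 53 (7/53 = 13.2%). The choice hardly matters. The AUC0-t interval gives a CV of about 17%, so Cmax is the sensitive variable.

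**Simulation.** 200,000 trials per setting; 36 subjects; log-normal data; within-subject SD 0.298; paired T−R differences (a simplification of the planned ANOVA). Assumptions not in the protocol: between-subject log-SD 0.30 to 0.45, and 80-125% limits for this study. Section 6.2.1 states those limits for the earlier study only. Passing means the 90% CI lies within the limits.

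For the error rates, the true T/R was set at a limit. Helpful direction means dropping the lowest Reference values at a true 125% and the highest at a true 80%.

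| Subjects removed on their Reference value | Chance of passing at a true limit |
|---|---|
| None | about 5% |
| One, most extreme in either direction | 5.3-5.6% |
| Two, most extreme in either direction | 5.6-6.0% |
| One, helpful direction | 6.7-7.4% |
| Two, helpful direction | 8.4-9.9% |

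**Shift in the estimate at a true ratio of 100%.** Dropping the lowest Reference subject moves the expected T/R to about 98.7-99.0%, and the lowest two to about 97.7-98.2%. Dropping the highest gives about 101.0-101.3% (one) or 101.9-102.4% (two). T1/R and T2/R share the same Reference values and so move together. T1/T2 stays at 100%.

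**One aberrant subject kept in.** If his Reference value is a fraction f of expected, T/R is multiplied by exp(−ln f / 36).
- f = 0.40: exp(0.916/36) = 1.026, a shift of 2.6%.
- f = 0.10: exp(2.303/36) = 1.066, a shift of 6.6%. This subject is not caught by the 5% AUC rule.

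The decision to keep or drop such a subject is therefore material either way.

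**The case against.** The strongest defence is that the rule carries real safeguards. An exclusion needs a scientific justification and the agreement of two parties, and the excluded data are assayed and listed. An assessor can therefore see each removal and re-run the analysis with everyone in. It would be too strong to infer that a justified exclusion could not be told from a convenient one. A blind data review might also sit in an SAP that is not at hand. What survives is that visibility does not protect the primary estimate or supply a criterion. An SAP could add a threshold, but it could not extend the rule to T1 and T2 without contradicting the protocol's closed list.

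Four stronger readings are tempting and are not supported:
- **An odd Reference profile removes the subject from T1 vs T2 as well.** Section 15.1.1 reads "PK set 3: all randomised subjects who fulfil the study protocol requirements in terms of T1 and T2 IMP intake" and ties evaluability to that comparison. Section 15.1.3 does not say that a Reference finding empties all three sets. Unlike section 15.1.2, it also does not limit itself to each comparison. This is an ambiguity to clear up.
- **The rule contradicts the case for an open-label design.** Section 9.2 says "The outcome variables are not influenced by the subjects or Investigator being aware of the administered products". That concerns subjects and the Investigator, not decisions on analysis sets by the CRO and the sponsor.
- **There is no yardstick at all.** Section 6.2 gives mean fed shifts and a half-life, and section 6.2.1 gives fasting Reference data. The standard is unquantified, not absent.
- **Error rates of 11% (one removed) or 19% (two) are the size of the problem.** They come from removing subjects whose Reference value disagrees most with their own Test value. The rule compares the Reference with an expected profile, so those figures describe a breach of it.

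**Conclusion.** The point holds in limited form. Section 15.1.3 fixes a Reference-only exclusion, without a threshold, decided after concentrations are known and with no requirement for blinding or timing. Followed as written, it can bias T1/R and T2/R; it does not necessarily do so.

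Applied without regard to direction, it leaves the mean ratio unchanged and moves the 5% error only to about 5.3-6.0%. Applied directionally, the error reaches about 6.7-7.4% with one subject removed and 8.4-9.9% with two. These sizes rest on a within-subject SD from a fasting study, an assumed between-subject SD, limits borrowed from the earlier study, and a paired analysis standing in for the full ANOVA. The defect in the text does not depend on them.

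Severity: should-fix.

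**What to change.** Preferred: delete the second bullet of section 15.1.3. Keep such subjects in the primary ANOVA and allow their removal only in a labelled sensitivity analysis.

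If a rule is kept: prespecify a numeric criterion, apply it equally to T1, T2 and R, have it decided blind to treatment before any ratio is computed, and report the all-subjects analysis beside it.

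In either case, add a sentence that a post-bioanalysis exclusion applies only to comparisons using the affected period, so that a Reference finding leaves PK set 3 untouched.

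The cost is about two sentences in section 15.1.3, matching SAP text and one extra table. The statistical downside of deletion is real. Section 15.1.2 catches only events that were noticed and recorded. An aberrant Reference profile that escapes both it and the 5% AUC rule stays in, widens the interval and can shift T/R by the 2.6% to 6.6% shown in the working. The sensitivity analysis is where that effect would be shown.
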